2 STUDY RATIONALE

2.1 Risk / Benefit Assessment

Risk of treatment with folinic acid: In a prior randomized controlled trial of the same dose and duration of treatment with folinic acid in 48 children with ASD, there were no serious side effects and no side effects that were more common with folinic acid than placebo treatment.

Folinic acid is closely related molecule to the B vitamin, folate. It is approved to help with the adverse of effects of certain medications such as methotrexate, which depletes folate in the body. Folinic acid is also approved to be used in combination with chemotherapeutic agents in certain cancers. The identification of side effects of folinic acid is somewhat confounded by the combined use of potent chemotherapeutic drugs. Adverse effects of folinic acid may include: skin rashes, itching, facial flushing, nausea or vomiting. Acute allergic reactions have been reported – but considered rare.

Potential benefits: There is a possibility that children enrolled in this study will experience some beneficial effects related to treatment with folinic acid. As noted above, in a prior study of folinic acid in ASD, children were noted to have improvements in aberrant behavior and language development. Also, adult studies have found improvement in mood in patients treated with supplements containing folinic acid. Finally, there is biological plausibility that children with impaired cerebral folate transfer may have some beneficial physiological, and therefore clinical, effects when cerebral folate levels are raised through folinic acid treatment.

3 STUDY OBJECTIVES

3.1 Primary Objective

The primary objective is to determine if there is a correlation between changes in behavior and changes in urinary metabolites in children with ASD who receive folinic acid treatment for 12 weeks. This will provide insight into the potential mechanism of action.

3.2 Secondary Objectives:

Secondary objectives include an examination of the correlation between changes in urinary metabolites and other outcome measures, including the Social Responsiveness Scale (SRS) (parents and teachers) and the Pediatric Quality of Life Inventory (PedsQL) (parents). It is possible that specific urinary metabolites are related to different clinical domains, and we will therefore examine correlations in each of these domains.

STUDY DESIGN

3.3 Study Overview

This is an open-label, 12-week study examining the effects of folinic acid on behavior in children with ASD and the correlation between behavior change and urinary metabolites.

Total duration of subject participation will be four months – 3 months while taking the study supplement and one month of wash-out. Total duration of the study is expected to be 12 months.

4 CRITERIA FOR EVALUATION

4.1 Primary Endpoint

- Correlation between changes in the Aberrant Behavior Checklist and urinary metabolites.

4.2 Secondary Endpoints

- Correlation between changes in all outcome measures and changes in urinary metabolites.

4.3 Safety Evaluations

- Patient reported adverse events, which will be collected through spontaneous reporting as well as specific queries at 1 and 3 months of treatment.

5 SUBJECT SELECTION

5.1 Study Population

Children and young adults between the ages of 5 and 22 who are enrolled at the Oak Hill School (OHS) in San Anselmo, CA (a school for children with autism or related neurodevelopmental disorders). OHS is the site for our ongoing outcomes study using a secure web-based outcome platform where enrolled children (n=40) have regular outcomes completed by teachers (weekly) and parents (quarterly) (UCSF CHR approval number 13-11086). A prior intervention study of the supplement, sulforaphane (UCSF CHR approval number 15-17002) demonstrated the feasibility of conducting an open-label study to examine changes in urinary metabolites and clinical measures with this population and the web-based outcome platform.

5.2 Inclusion Criteria

1. Male or female, enrolled at OHS, age 5-22 and with a diagnosis of ASD.
2. ASD diagnosis is established DSM-IV criteria, child observation by an expert clinician, and score on the Social Communication Questionnaire, completed by parents).

3. Written informed consent obtained from the subject's legal representative and ability for subject to comply with the requirements of the study.

5.3 Exclusion Criteria

1. Presence of a condition or abnormality that in the opinion of the Investigator would compromise the safety of the patient or the quality of the data.
2. Known allergy to any component of the folic acid product.

6 CONCURRENT MEDICATIONS

All subjects should be maintained on the same medications throughout the entire study period, as medically feasible, with no introduction of new chronic therapies.

6.1 Prohibited Medications and Treatments

Study subjects must not currently be taking folic acid or have used this supplement in the last 6 months.

7 STUDY TREATMENTS

Since this is an open-label study, all subjects will receive folic acid. Subjects, parents, teachers, and clinicians are not blinded to treatment status. There is no control product being used.

7.1 Formulation of Product –

Folic acid is prepared as a calcium salt. The capsules are dye-free, milk-product free, and vegetarian and are provided in 10 mg available for weight-based dosing (2mg/kg with maximum dose of 50mg/day divided in two doses). The capsules are produced by Lee Silsby Pharmacy (Cleveland Heights, OH). Certificate of analysis has been obtained by an independent analytical service and is part of the IND packet, approved by the FDA.

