PRIMARY OBJECTIVE	To examine changes in urinary metabolites in children with ASD being treated with folinic acid and to determine if changes in urinary metabolites are correlated with clinical improvements.
SECONDARY OBJECTIVES	Develop a prediction model to determine which children are most likely to benefit from folinic acid.

NUMBER OF SUBJECTS	40
SUBJECT SELECTION CRITERIA	
Inclusion Criteria: Age 5-22, enrolled at Oak Hill School, diagnosis of autism established by DSM-IV criteria and clinician examination.
 
Exclusion Criteria: Seizure disorder, serious medical illness within the last 6 months as judged by the study PI. Known allergy to folate.

TEST PRODUCT, DOSE, AND ROUTE OF ADMINISTRATION	Folinic acid 2mg/kg per day (maximum 50mg/day) in two equally divided doses with half the target dose given during the first 2 weeks.
CONTROL PRODUCT, DOSE AND ROUTE OF ADMINISTRATION	There is no control product in this study.
DURATION OF SUBJECT PARTICIPATION AND DURATION OF STUDY	
Subjects will be on study for 4.5 months
 
Screening: up to 2 weeks.
 
Treatment: 3 months
 
Follow-up: 1 month (1 additional month after treatment)
 
The total duration of the study is expected to be 12 months. 3-6 months for subject recruitment; 4 months for final subject follow-up; 2 months for data analysis and manuscript preparation.

CONCOMITANT MEDICATIONS	
Allowed: all
 
Prohibited: none

EFFICACY EVALUATIONS	
Parent (Aberrant Behavior Checklist, Social Responsiveness Scale, Pediatric Quality of Life)
 
Teacher (Student Progress Form, Aberrant Behavior Checklist, Social Responsiveness Scale)
 
Urinary Metabolomics (Baseline and 3 months)

PRIMARY ENDPOINT	
 Correlation between mean change in Aberrant Behavior Checklist and mean change in urinary metabolites.
SECONDARY ENDPOINTS	
 Correlations between changes in urinary metabolites and all secondary outcome measures.
OTHER EVALUATIONS	None

SAFETY EVALUATIONS	All study subjects are enrolled at the Oak Hill School and will be observed all school days by teachers, who are aware of student participation in the study. Parents, teachers, and enrolled students will be advised to report any new medical problems to study investigators, who will evaluate all potential adverse events and report to the CHR according to established guidelines.

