7.1.1 Dosage/Dosage Regimen -

Study participants will receive weight-based dosing (2mg/kg per day) divided in 2 equal doses with maximum daily dose of 50mg. If unable to swallow, the capsules may be administered by piercing the capsule and mixing the contents into soft food including yogurt, oatmeal, drinks.

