7.1.3 Administration Instructions

Each participant will be instructed to take the weight-based dose, by mouth twice a day with meals.

Doses may be mixed with liquid or soft foods.

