12 PROTOCOL VIOLATIONS

A protocol violation occurs when the subject, or investigator, fails to adhere to significant protocol requirements affecting the inclusion, exclusion, subject safety and primary endpoint criteria. Protocol violations for this study include, but are not limited to, the following:

- Failure to meet inclusion/exclusion criteria.
- Improper use of schedule/dose of study supplement.

When a protocol violation occurs, it will be discussed with the investigator and a Protocol Violation Form detailing the violation will be generated. This form will be signed by the Investigator and reported to the UCSF CHR according to established guidelines.

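### The capsule strength, equal split and daily maximum do not fit together for participants of 25 kg or more, and the half-dose start appears only in the synopsis

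*Combined protocol and SAP*

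**What the plan says.** The dosing instructions are spread over four places in the combined protocol and SAP.

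- **Section 7.1** gives the product: "provided in 10 mg available for weight-based dosing (2mg/kg with maximum dose of 50mg/day divided in two doses". No second strength is named anywhere.
- **Section 7.1.1** gives the regimen: "weight-based dosing (2mg/kg per day) divided in 2 equal doses with maximum daily dose of 50mg". It adds: "If unable to swallow, the capsules may be administered by piercing the capsule and mixing the contents into soft food".
- **Section 7.1.3** gives the instruction to families: "Each participant will be instructed to take the weight-based dose, by mouth twice a day with meals". It continues: "Doses may be mixed with liquid or soft foods".
- **The protocol synopsis** (test product row) gives the same 2 mg/kg/day and 50 mg maximum, "in two equally divided doses with half the target dose given during the first 2 weeks".

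Two other sections bear on this. Section 7.2.1 has staff record capsules dispensed and returned, and Section 9.4 adds collection of a medication diary. Section 12 lists "Improper use of schedule/dose of study supplement" among protocol violations.

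**The concern.** A dose set per kilogram and capped must be turned into a number of capsules by whoever dispenses it. If the stated strength, split and maximum cannot all be met with whole capsules and no rule for part capsules is given, staff must choose which instruction to relax. The documents do not record that choice.

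The half-dose start raises a separate question. A reader following the treatment sections would start a child on the full weight-based dose, while a reader following the synopsis would start on half of it.

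Three things are at stake: what participants actually receive, whether the capsule count can be compared with a planned dose, and what counts as a dose deviation under Section 12. The study seeks a mechanism by relating each participant's metabolite change to behavior change, so exposure should at least be known for each participant.

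**Working it through.** The plan states no capsules-per-dose figure, so there is none to reproduce. The check is direct arithmetic.

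**Inputs**
- Capsule strength: 10 mg (7.1).
- Daily target: 2 mg/kg, maximum 50 mg, in two equal doses (synopsis, 7.1.1).
- Half the target for the first 2 weeks (synopsis only).
- Treatment length: 12 weeks (Section 3.1).
- Participant weights: not given; only ages 5 to 22 (5.2).

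**Formulas**, with w the weight in kg
- Daily target T = min(2w, 50) mg.
- Each full dose = T/2; each dose in the half-dose phase = T/4.
- Capsules per dose = that amount / 10.

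**Where the maximum applies.** 2w = 50 gives w = 25 kg.

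| Weight | T (mg/day) | Full dose: mg (capsules) | Half-dose phase: mg (capsules) |
|---|---|---|---|
| 15 kg | 30 | 15 (1.5) | 7.5 (0.75) |
| 18 kg | 36 | 18 (1.8) | 9 (0.9) |
| 20 kg | 40 | 20 (2) | 10 (1) |
| 22 kg | 44 | 22 (2.2) | 11 (1.1) |
| 25 kg or more | 50 | 25 (2.5) | 12.5 (1.25) |

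**Whole-capsule options at the maximum.** Two equal doses of whole 10 mg capsules require a daily total that is a multiple of 20 mg.
- Against 50 mg/day: 40 gives (40 − 50)/50 = −20%; 60 gives (60 − 50)/50 = +20% and exceeds the stated maximum.
- Against 25 mg/day in the half-dose phase: 20 gives (20 − 25)/25 = −20%; 40 gives (40 − 25)/25 = +60%.
- 20 mg plus 30 mg keeps 50 mg/day with whole capsules, but the doses are unequal.

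So no whole-capsule regimen at the maximum meets the equal split and the 50 mg total together.

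**Below 25 kg.** Each full dose in mg equals the weight in kg. Most weights give a fraction of a capsule, as any per-kilogram dose with a fixed strength will. What is missing here is a rounding rule.

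**Size of the starting-dose disagreement.** For a participant at the maximum, over 12 weeks (84 days):
- Without the half-dose phase: 84 × 50 = 4,200 mg, or 420 capsules.
- With it: 14 × 25 + 70 × 50 = 3,850 mg, or 385 capsules.
- Difference: 350 mg, or 35 capsules; 350/4,200 = 8.3% of the total.

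During the first two weeks the two readings differ by a factor of two.

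**The case against.** The strongest reply is that the documents contain a gap in instructions rather than an impossibility.

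- **A reader might infer that the dose cannot be given at all.** The documents do not support that. Nothing says doses must be whole capsules. Section 7.1.1 lets a capsule be opened for someone who cannot swallow it, and 7.1.3 lets any participant's dose be mixed with food. A part capsule is therefore not ruled out. However, both sections describe how to take a dose, not how to measure a half or quarter of a capsule.
- **A reader might infer that nearly every child is affected.** No weights are given, and below 25 kg ordinary rounding could serve. The half-dose phase is also workable for some: at 20 kg it is one capsule twice daily. The firm conflict is confined to 25 kg and above.
- **The sentence in 7.1 reads as if words are missing**, and product details sit in an IND packet that is not part of these documents. Another strength may have been intended. This limits certainty about the product, but the text as it stands still needs correcting.
- **A reader might infer that capsule counts become useless.** They do not: counts and the diary can be checked against whatever each family was told. What is lost is the link from that instruction to the protocol's planned dose.
- **The effect on exposure may be modest.** The maximum already makes mg/kg fall with weight: 50 mg is 2 mg/kg at 25 kg and 1 mg/kg at 50 kg. One consistent rule would give all capped participants the same amount, and the analyses in 13.1 and 13.2 do not use dose. This stands, provided that one rule is in fact applied.
- **Whether rounding by staff would be a violation under Section 12** is a matter of interpretation; the section does not say so.

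None of this removes the mismatch at the maximum, and none of it explains why the half-dose start is missing from the treatment sections.

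**Conclusion.** The point holds for two defects.

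1. At 25 kg and above, the named capsule strength, the equal split and the daily maximum cannot all be met with whole capsules, and no rule for part capsules, rounding or unequal doses is given. Equal whole-capsule doses would miss the 50 mg total by 20% in either direction, and the higher option breaches the stated maximum.
2. The synopsis and the treatment sections disagree on the dose for the first two weeks, by a factor of two at any weight.

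The first conclusion assumes that 10 mg is the only strength supplied, as the text implies. How many participants it touches is unknown; a large share at 25 kg or more is plausible for ages 5 to 22 but is not documented. The second rests on the text alone. Neither invalidates the planned correlation analysis, but both bear on what participants receive and should be corrected.

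**What to change.** The sponsor should reconcile capsule strength, equal split, daily maximum and half-dose phase so that the synopsis and Sections 7.1, 7.1.1 and 7.1.3 say the same thing. The protocol should then state the dispensing rule actually used, including how any part capsule or rounding is handled, ideally as a table by weight. Milligrams dispensed should be recorded for each participant, so that the counts in 7.2.1 can be compared with the planned dose. Which figures stand is for the sponsor to decide.

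The cost is a wording amendment, approved under Section 15.1, together with a dispensing table and one added data item. Sample size, visits and planned analyses are unchanged.

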7.1.1 Dosage/Dosage Regimen -

Study participants will receive weight-based dosing (2mg/kg per day) divided in 2 equal doses with maximum daily dose of 50mg. If unable to swallow, the capsules may be administered by piercing the capsule and mixing the contents into soft food including yogurt, oatmeal, drinks.

7.1.2 Dispensing

Study staff will dispense the study supplement, labelled with each participant's unique study ID number, after the participant has completed all necessary enrollment procedures.

7.1.3 Administration Instructions

Each participant will be instructed to take the weight-based dose, by mouth twice a day with meals.

Doses may be mixed with liquid or soft foods.

7.2 Supply of Study Supplement at the Site

The study supplement will be stored by the study site at controlled room temperature, 20 to 25°C (68 to 77°F). Participants will be instructed to also store the product at room temperature, consistent with labelled instructions and stability testing.

7.2.1 Study Supplement Accountability

An accurate and current accounting of the dispensing and return of study supplement for each participant will be maintained on an ongoing basis by a member of the study site staff. The number of study supplement capsules dispensed and returned by the participant will be recorded.

8 STUDY PROCEDURES AND GUIDELINES

A Schedule of Events representing the required testing procedures to be performed for the duration of the study is diagrammed in Appendix 1.

8.1 Clinical Assessments

8.1.1 Concomitant Medications

All concomitant medication and concurrent therapies will be documented at the Screening visit. Dose, route, unit, frequency of administration, and indication for administration and dates of medication will be captured.

8.1.2 Demographics

Demographic information (date of birth, gender, race) will be recorded at the Screening visit.

8.1.3 Medical History

Relevant medical history, including history of current disease and information regarding underlying diseases will be recorded at Screening visit.

8.1.4 Adverse Events

Information regarding occurrence of adverse events will be captured throughout the study. Participants will be informed to contact a study staff member if they experience a new medical problem – this information will be recorded on an Adverse Event form (including entries for duration, severity, outcome, treatment and relation to study supplement). AE forms will be reviewed by a study investigator and reported to the UCSF CHR according to established guidelines. We will be carefully monitoring patients for the occurrence of any adverse events through active questioning and 1 and 3 months as well as instructions for patients to report any new medical problem immediately to a study team member. All adverse events will be reviewed by a study investigator within 24 hours and reported to the Committee on Human Research according to standard guidelines.

8.2 Clinical Laboratory Measurements

Urinary Metabolomic Profile – all participants will have urine collected (fasting, 8am target collection time) at Screening and Close-out (3 months). Urine will be stored in sterile containers at -80 degrees Celsius and analyzed in one batch after all participants have completed the study. Metabolomic assessment will be conducted by Metabolon (Research Triangle, NC). Metabolon is one of the largest and most established laboratories conducting state-of-the art metabolomics assessments of urine, plasma, and other clinical samples. Metabolon has 160 employees including more than 40 PhDs with diverse backgrounds in molecular biology, biochemistry, bioinformatics, and statistics. They have completed over 4,000 metabolomic projects for over 700 clients. Their analyses have been used in more than 500 peer-reviewed publications including numerous articles in *Cell*, *Nature*, and *Science*. (www.metabolon.com)

9 EVALUATIONS BY VISIT

9.1 Visit 1: Screening visit – this visit will involve a face-to-face meeting with the study participant and their parent/legal guardian. A study team member will explain the entire study and obtain signed informed consent. Study inclusion/exclusion criteria will be reviewed and eligible participants will go on to complete all screening activities as below.

1. Review the study with the participant and obtain written informed consent.
2. Assign the participant a unique study ID number
3. Record demographics data.
4. Record medical history.
5. Record concomitant medications.
6. Collect urine specimen.
7. Dispense study supplement
8. Schedule subject for Baseline visit
9. Record study subject weight

9.2 Visit 2 (Baseline) – NOTE – for this study, which will take place at the Oak Hill School, all enrolled children will begin the study supplement on the same date (exact day TBD based on parent/teacher schedules and CHR approval date). This will improve the logistics of the study because teachers regularly complete outcome assessments using our established on-line outcomes platform at quarterly intervals (that match their school-based quarterly progress reports). This “batch” enrollment of participants has several advantages: 1) all participants will begin and end on the same date, which we believe will support the overall study compliance and enthusiasm, as all children/families will be involved in the study at the same time; 2) outcome assessments are a natural part of the study schedule, since they normally are completed by the teachers at 3 months intervals and will therefore occur as children complete the 3-month treatment; 3) compliance and reminders to parents/guardians and teachers will be simplified, since all participants will be on the same schedule and all

reminders can be sent in batches; 4) variation from time/season effects will be minimized, since all children will be experiencing the same school environment at the same period in the study.

1. Parents complete Baseline Outcome Measures.
2. Teachers complete Baseline Outcome Measures.
3. Subject starts taking study supplements at this time.
4. Reinforce study directions, contact information, emphasize need to report new medical problems (possible AE's).

9.3 Visit 3: Follow-up 1(one-month visit): TBD

1. Parents complete Follow-up Outcome Measures.
2. Teachers complete Follow-up Outcome Measures.
3. Adverse event form completed by parents, reviewed by study investigators.
4. Study supplement instructions reviewed.

9.4 Visit 4: Follow-up visit 2 (three month visit): TBD

1. Parents complete Follow-up Outcome Measures.
2. Teachers complete Follow-up Outcome Measures.
3. Adverse event form completed by parents, reviewed by study investigators.
4. Urine collected (fasting, 8am specimen, stored at -80 degrees Celsius)
5. Study supplement stopped. Medication diary and used and unused study supplement bottle collected and counted.
6. Record study subject weight.

**9.5 Visit 5 Follow-up visit 3 (four month visit, one-month off study supplement):
TBD**

1. Parents complete Follow-up Outcome Measures.
2. Teachers complete Follow-up Outcome Measures.

